- L:** Beginning with the Week 25 Visit and throughout Treatment Period 2, subjects who experience ≥ 3 HAE attacks (as determined per protocol) within an 8-week evaluation period are eligible for CSL830 dose increases in increments of 20 IU/kg (up to a maximum dose of 80 IU/kg). All CSL830 dose increases are optional, and will be made only in subjects who are eligible, at the sole discretion of investigator. An evaluation period for any dose increase is defined as beginning after a dose-stable period (ie, 2 weeks after the initiation or dose increase of CSL830). See [Section 3.2](#) for additional details.
- M:** The subject eDiary will not be collected from subjects at the last visit of Treatment Period 2 (Follow-up Visit) if they plan to participate in the Extension Period.

Schedule of Laboratory Assessments for “CSL830-Continuation” Subjects ^A

	Treatment Period 1							Treatment Period 2							Follow-up ^B
Week	1	5	9	13	17	21	25	29	33	37	41	45	49	53	See Footnote B.
Day	1	29	57	85	113	141	169	197	225	253	281	309	337	367	
Window (days)		± 2	± 2	± 2	± 2	± 2	± 2	± 2	± 2	± 2	± 2	± 2	± 2	± 2	
Study center visit	X		X		X		X	X		X		X		X	X
Telephone contact		X		X		X			X		X		X		
Blood samples: • Hematology • Biochemistry • Coagulation	X ^C		X				X	X		X				X	
CCI	X ^D		X				X	X		X				X	
Blood sample for anti-C1-INH antibody	X ^C						X							X	
Blood sample for viral serology	X ^C						X							X	
Urine sample for urinalysis	X ^C		X				X	X		X				X	
Urine sample for pregnancy test ^E	X		X				X			X				X	

C1-INH = C1-esterase inhibitor; CCI [redacted]; CCI [redacted].

Notes to the Schedule of Laboratory Assessments for “CSL830-Continuation” Subjects:

- A:** “CSL830-Continuation” Subjects are subjects who complete participation in study CSL830_3001 and who continue directly on to participate in the current study (ie, ≤ 1 week between the End of Study Visit of CSL830_3001 and the first visit of CSL830_3002 Treatment Period 1).
- B:** Subjects will attend a Follow-up Visit occurring 14 days (± 3 days) after the final visit in Treatment Period 2 or any visit resulting in study discontinuation, unless informed consent/assent has been withdrawn or if the Extension Period starts prior to the scheduled Follow-up Visit.
- C:** If these assessments are or have been conducted at the CSL830_3001 End of Study Visit, then they do not need to be repeated here.
- D:** CCI [redacted]

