Urine Pregnancy Test ^A
Confirm Access to On-demand HAE Medication
CSL830 Accountability
Concomitant Medication
Adverse Events

Abbreviations: DVT = deep vein thrombosis; HAE = hereditary angioedema; PE = pulmonary embolism.

^A The results of the urine pregnancy test can only be used to satisfy the applicable eligibility criterion if the Treatment Period 2 End of Study Visit and the first visit of the Extension Period (ie, Day 367) occur on exactly the same day. Otherwise, a new pregnancy test must be performed at the first study visit in the Extension Period in order to confirm eligibility.

8.4.6.2 Extension Period Week 6

Subjects will be contacted by telephone at the Extension Period Week 6 Visit (± 2 days) to record AEs and concomitant therapies and self-administer the AE QoL questionnaire.

8.4.6.3 Extension Period Week 12

Subjects will attend a study visit at Extension Period Week 12 (± 2 days).

The following procedures will be performed by the investigator or delegate:

- Vital signs including weight.
- Assess risk of DVT and PE.
- CCI [Redacted]
- CCI [Redacted]
- CCI [Redacted]
- CCI [Redacted]

- [REDACTED]
- Review subject eDiary; record information on HAE attacks in eCRF.
 - Perform CSL830 accountability.
 - Confirm access to on-demand medication for the treatment of breakthrough HAE attacks.
 - Record AEs.
 - Record concomitant therapies.
 - Dispense CSL830/study supplies to subject.
 - Schedule the next telephone contact and the next study visit.

8.4.6.4 Extension Period Week 18

Subjects will be contacted by telephone at the Extension Period Week 18 Visit (± 2 days) to record AEs and concomitant therapies.

8.4.6.5 Extension Period Week 22

Subjects will self-administer the AE QoL questionnaire at Extension Period Week 22 (± 2 days).

8.4.6.6 Extension Period Week 24

Subjects will attend a study visit at Extension Period Week 24 (± 2 days).

The following procedures will be performed by the investigator or delegate:

- Vital signs including weight.
- Physical examination.
- Assess risk of DVT and PE.
- Obtain blood sample for assessment of antibodies against C1-INH.
- For female subjects, obtain urine sample for dipstick pregnancy testing.
- Review subject eDiary; record information on HAE attacks in eCRF.
- Perform CSL830 accountability.
- Confirm access to on-demand medication for the treatment of breakthrough HAE attacks.
- Record AEs.
- Record concomitant therapies.
- Dispense CSL830/study supplies to subject.

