8.4.6.22 Extension Period Week 88 (Final Visit)

Subjects will attend a study visit at Extension Period Week 88 (± 2 days).

The following procedures will be performed by the investigator or delegate:

- Physical examination.
- Vital signs including weight.
- Assess risk of DVT and PE.

- CCI [REDACTED]
- CCI [REDACTED]
- CCI [REDACTED]
- Obtain blood samples for the following:
 - ALT/AST
 - Coagulation.
 - Viral serology.
 - Assessment of antibodies against C1-INH.
- CCI [REDACTED]
- Obtain a urine sample for urinalysis.
- Indwelling venous catheter is present (yes/no) [if status has changed, then provide a reason for the change (where available) and date of change (where available), and cross-check with AEs recorded in the eCRF for consistency (where applicable)].
- For female subjects, obtain urine sample for dipstick pregnancy testing.
- Review subject eDiary; record information on HAE attacks in eCRF.
- Perform CSL830 accountability.
- Confirm access to on-demand medication for the treatment of breakthrough HAE attacks. The subject will be advised to resume usual medical care upon completion of the study
- Record AEs.
- Record concomitant therapies.
- Schedule the next telephone contact.
- Collect eDiary.

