11.3.3.2 Secondary Safety Analyses

Adverse event data will be presented in individual listings and summary tables.

The number and percentage of subjects experiencing SAEs, temporally-related AEs, increased risk scores for DVT or PE, thromboembolic events, inhibitory anti-C1-INH antibodies, or clinically significant abnormalities in laboratory assessments during treatment will be summarized as defined above in [Section 11.3.3](#) and overall. The number and percentage of subjects who become seropositive for HIV-1, HIV-2, HBV, or HCV will be summarized as defined above in [Section 11.3.3](#) and overall. The number and percentage of subjects experiencing solicited local AEs, the number of solicited local AEs, and the number of solicited local AEs per administration will be summarized as defined above in [Section 11.3.3](#) and overall. The number and percentage of administrations of CSL830 resulting in solicited local AEs will be summarized as defined above in [Section 11.3.3](#) and overall. An overall summary of AEs will be given.

Temporally-related AEs will be defined as AEs which began within 24 hours of administration of CSL830. Note that temporally-related AEs are referenced as “suspected ADRs” in study CSL830_3001. Temporally-related AEs occurring during treatment will be summarized as defined above in [Section 11.3.3](#) and overall in the current study (CSL830_3002).

Summaries will include the number and percentage of subjects, the number of AEs, and the number of AEs per administration and per week (where applicable) and will also be summarized as defined above in [Section 11.3.3](#) and at study visits. Summaries by SOC and PT will also be presented.

Adverse events will also be described by intensity, relationship to CSL830, duration, and seriousness.

The safety analyses will be conducted for Treatment Period 1 (only), Treatment Period 2 (only), and for Treatment Period 1 and 2 (together). For the subjects who are in the Extension Period, the safety analyses will be conducted for the Extension Period and for the treatment periods overall.

11.3.4

CCI [Redacted]

CCI [Redacted]

CCI [Redacted]

[Redacted]

[Redacted]

CCI [Redacted]

[Redacted]

[Redacted]

[Redacted]

[Redacted]

CCI [Redacted]

[Redacted]

[Redacted]

[Redacted]

CCI [Redacted]
CCI [Redacted]

[Redacted]
[Redacted]

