4.7.2.1 Method of analysis for secondary safety endpoints

The AE tables will comprise two type of tables, one for number of subjects experiencing a particular AE, percentage of subjects based on the Safety Population, and number of events and the other type of tables for number of events per subject-injections and number of events per subject-years, the latter giving exposure-adjusted rates (per injection and per year).

All AEs

A summary of all AEs will be given presenting: number and percentage of subjects with AEs, with temporally-related AEs, with suspected ADRs, with SAEs, with related AEs, AE leading to discontinuation based on AE start date with subcategories for “related” and “not related”, with each severity and with each outcome of AEs. Analogue summaries will be provided for only SAEs and for only non-serious AEs.

The following tables will be generated for all AEs (including unsolicited AEs and solicited AEs):

- Incidence of subjects with AEs by SOC and PT.
- Incidence of subjects with SAEs by SOC and PT.
- Incidence of subjects with AEs by severity, SOC, and PT.
- Incidence of subjects with AEs by relationship to investigational product, SOC, and PT.
- Incidence of subjects with AE leading to discontinuation based on adverse event start date by SOC and PT.
- Incidence of subjects temporally-related AEs by SOC and PT.
- Incidence of subjects with suspected ADRs by SOC and PT

- Incidence of subjects with AE matching the PT ‘Embolic and Thrombotic Events’ (SMQ) by SOC and PT overall and split by subjects with versus without indwelling venous catheter. Events identified by this SMQ PT are reviewed by CSL Behring to assist in identification of cases of TEEs.

- Incidence of subjects with AE High Level Term ‘Sepsis, Bacteraemia, Viraemia and Fungaemia NEC’ (by SOC and PT, overall and split by subjects with vs. without venous catheter). Events identified by this High Level Term are reviewed by CSL Behring to assist in identification of cases of sepsis and/or bacteremia events.

- Incidence of subjects with SMQs to identify anaphylaxis defined as severe and clinically relevant systemic allergic reaction with sudden onset and rapid progression by SOC and PT. AE terms screened to assist in identification of cases of anaphylaxis were selected for review using the following SMQs:
 - SMQ = ‘Anaphylactic reaction (SMQ)’ and selection = ‘Broad’.
 - SMQ = ‘Anaphylactic/anaphylactoid shock conditions (SMQ)’ and selected = ‘Broad’.

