4.7.2.3 Analysis of Laboratory Findings

Normal ranges will be provided for laboratory tests. Values outside the normal range will be judged as clinically significant or non-clinically significant by the investigator. All abnormal laboratory data considered as clinically significant will be presented as AE.

All continuous laboratory parameters will be plotted against their scheduled assessments visits.

Analyses of haematology, biochemistry, and coagulation parameters will consist of the following:

- Descriptive statistics for baseline and each treatment visit, including changes from baseline to each treatment visit
- Mean values and the SD of the continuous laboratory parameters at each scheduled visit will be plotted against scheduled visits.

Baseline will be the assessment before the first injection (Week 1 Day 1) for all “CSL830-Naïve” and “CSL830-Interrupted” Subjects and “CSL830-Continuation” Subjects who did not complete the assessments at the CSL830_3001 End of Study Visit. For “CSL830-Continuation” Subjects who complete the assessments at the CSL830_3001 End of Study Visit, these assessments will be the baseline. If the baseline value for a subject is missing, no change from baseline will be calculated for the subject.

The number and percentage of subjects without anti-C1-INH antibodies and with anti-C1-INH antibodies (inhibitory, non-inhibitory and inhibitory and non-inhibitory combined) during the study will be summarized overall and for each study visit

Urinalysis, viral serology and pregnancy testing results will be listed only.

Notes:

- All results outside predefined normal ranges will be flagged as high or low in the data listings.
- Clinically significant laboratory values will be flagged in the listings.
- Unscheduled results will be listed only and not included in summary tables.

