4.14 Changes in Conduct or Planned Analyses from the Protocol

The statistical analysis for the original protocol and the Extension Period amendment are described in the one SAP to be on hand and not in two different statistical analysis plans.

The data from Treatment Period 1, Treatment Period 2, and Extension Period will be analyzed and presented jointly. Data collected from subjects who are enrolled in the Extension Period will be analyzed together with the data of subjects who are not participating in the Extension Period.

Because of the assumption that a minority (e.g., less than 20%) of subjects will undergo a CSL830 dose increase during the study, the first and second approaches as specified in 11.3.3 of the protocol will not be performed for the secondary safety endpoints. Rather, the approach to safety analysis based upon the actual treatment (40 IU/kg CSL830, 60 IU/kg CSL830 and ≥ 40 IU/kg CSL830) at the time of the event will be performed for the safety analyses.

The analyses by subjects who are randomized to 40 IU/kg CSL830 and who have 1 dose increase; by subjects who are randomized to 40 IU/kg CSL830 and who have 2 dose increases; by subjects who are randomized to 60 IU/kg CSL830 and who have 1 dose increase will not be done.

A treatment group ≥ 40 IU/kg CSL830 has been added in the analyses by treatment and overall group has been deleted.

If an event or evaluation occurred while a subject was receiving 80 IU/kg, these data will be listed and summarized in the ≥ 40 IU/kg CSL830 treatment group.

Adverse events that occur during the Screening will not be summarized for subjects in the Safety Population and will only be listed.

Safety and some efficacy analyses will not be performed for age group. No subgroups of subjects who previously used intravenously administered C1-INH for routine (long-term) prophylaxis will be assessed.

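### Laboratory sampling thins sharply in the Extension, yet the SAP pools Extension time into exposure-adjusted AE rates, so rates of laboratory-derived AEs are diluted by the schedule

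*SAP*

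**What the plan says.** **Sampling in Treatment Periods 1 and 2.** The Schedules of Laboratory Assessments give one row for "Blood samples: • Hematology • Biochemistry • Coagulation" and one for "Urine sample for urinalysis". Both are marked at Day 1 and at Weeks 9, 25, 29, 37 and 53, which is five post-baseline samples per subject.

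**Sampling in the Extension (Protocol 8.4.6, readable text).** At Weeks 24 and 72 the only blood item listed is "Obtain blood sample for assessment of antibodies against C1-INH". Week 48 lists ALT/AST, coagulation, antibodies and viral serology. Week 88 lists the same four and adds "Obtain a urine sample for urinalysis", the only Extension urinalysis. No readable Extension visit lists hematology, or any biochemistry other than ALT and AST.

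**How laboratory findings enter the AE tables.** SAP 4.7.2.3 states: "All abnormal laboratory data considered as clinically significant will be presented as AE". SAP 4.7.2.1 then gives "number of events per subject-injections and number of events per subject-years, the latter giving exposure-adjusted rates (per injection and per year". SAP 4.4.1 counts exposure up to the Week 88 Visit for Extension subjects, leaving out only a rest period and the final follow-up.

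**Pooling.** SAP 4.14 states: "The data from Treatment Period 1, Treatment Period 2, and Extension Period will be analyzed and presented jointly". The protocol had planned something different in 11.3.3.2: "For the subjects who are in the Extension Period, the safety analyses will be conducted for the Extension Period and for the treatment periods overall". Protocol 11.3.3 likewise calls for an Extension-only safety summary, kept apart from the earlier periods.

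**The concern.** A rate per subject-year is interpretable when events have a similar chance of being found throughout the time counted. For hematology and most of biochemistry, the readable Extension schedule offers no planned test, while every Extension subject adds up to 88 weeks to the denominator. Only a test done for clinical reasons can add to the numerator. The per-injection rate has the same defect, because dosing continues twice weekly.

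Long-term safety is the primary objective, and clinically significant laboratory abnormalities are part of a named secondary safety endpoint (Protocol 2.2.2). A pooled rate that is low because testing stopped could be read as reassurance about long exposure. Under the protocol's separate Extension summary a reader could at least see the rate drop where sampling drops; under joint presentation the drop is blended in. Neither document adjusts for it or footnotes it.

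**Working it through.** The documents state no sampling intensity and no expected laboratory AE rate, so there is no figure of the plan's own to reproduce on this point. The stated durations do add up: 4 + 52 + 2 = 58 weeks, and 58 + 88 = 146 weeks.

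**Inputs**
- Treatment Periods 1 and 2: Day 367 at Week 53 (Protocol 3.3), so 367 / 365.25 = 1.005 years.
- Extension: Day 617 at Week 88 (Extension schedule), so 617 / 365.25 = 1.689 years.
- Subjects: 100 completing Treatment Periods 1 and 2 (Protocol 11.1) and about 50 in the Extension (Protocol 3.5). Time from early withdrawals is ignored.
- Post-baseline samples per subject: 5 in Treatment Periods 1 and 2. In the Extension, s = 0 for hematology and other biochemistry, 1 for urinalysis, and 2 for coagulation and ALT/AST.

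**Formulas**
- Treatment Periods 1 and 2: 5 / 1.005 = 4.98 samples per subject-year.
- Pooled time: 100 × 1.005 + 50 × 1.689 = 184.9 subject-years, of which the Extension is 84.5 (46%).
- Pooled intensity: (100 × 5 + 50 × s) / 184.9.
- Fall: 1 − pooled intensity / 4.98.

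| Panel | Periods 1 and 2, per year | Extension, per year | Pooled, per year | Fall |
|---|---|---|---|---|
| Hematology; biochemistry other than ALT/AST | 4.98 | 0 | 500 / 184.9 = 2.70 | 46% |
| Urinalysis | 4.98 | 1 / 1.689 = 0.59 | 550 / 184.9 = 2.97 | 40% |
| Coagulation; ALT/AST | 4.98 | 2 / 1.689 = 1.18 | 600 / 184.9 = 3.24 | 35% |

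**Extension enrollment.** With 30 to 70 Extension subjects instead of 50, the falls are 34–54%, 30–48% and 26–41%.

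**Redaction.** Some items at Extension Weeks 12, 36 and 60 are blacked out. Suppose each of those visits hides a full panel, so that s rises by 3. Pooled intensity becomes 650 / 184.9 = 3.51, 700 / 184.9 = 3.79 and 750 / 184.9 = 4.06. The ratios to 4.98 are 0.706, 0.761 and 0.815, so the falls are 29%, 24% and 18.5%. The direction is unchanged.

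**Antibodies.** Anti-C1-INH antibodies are sampled post-baseline at Weeks 25 and 53, then at Extension Weeks 24, 48, 72 and 88. That is 2 / 1.005 = 1.99 per year against 4 / 1.689 = 2.37 per year, so this sampling does not thin.

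**Dose columns.** Assume 55 subjects per arm, 20% (11) raised at Week 25, and 25 per arm in the Extension. A raised subject then has 168 days at the starting dose and 199 days at the next in Treatment Periods 1 and 2.
- Treatment Period 1 and 2 time at 40 IU/kg: 44 × 367 + 11 × 168 = 17,996 days. With equal Extension uptake, 20 of the 25 stay at 40 IU/kg, adding 20 × 617 = 12,340 days. The share under the fuller schedule is 17,996 / 30,336 = 59%.
- Treatment Period 1 and 2 time at 60 IU/kg: 17,996 + 11 × 199 = 20,185 days. Extension time is (20 + 5) × 617 = 15,425 days. The share is 20,185 / 35,610 = 57%.
- If every raised subject enters the Extension, the 40 IU/kg share becomes 17,996 / (17,996 + 14 × 617) = 68%. The 60 IU/kg share stays at 57%, since 14 + 11 = 25.

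**The case against.** **The controlling table cannot be read.** Protocol 10.3 sets Extension laboratory time points by the Extension schedule table, and its laboratory rows are not in the available text. The visit narrative is an imperfect substitute: Week 84, for example, omits the recording of AEs that most other on-site visits list. This stands as a limit. The statement about what the Extension schedules holds for the readable text, and the redaction check covers Weeks 12, 36 and 60 only.

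**Event rates need not fall as far as sampling.** Protocol 10.3 allows clinically indicated tests, Protocol 8.4.7 allows unscheduled visits, and a persistent abnormality could still be caught at Week 48 or 88 for the panels sampled there. This stands. A reader might infer that laboratory AEs have almost no chance of detection in the Extension, and that the pooled rate is too low by the full share of Extension time. The documents do not support that.

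**The reach is narrow.** The protocol's laboratory endpoint is a percentage of subjects. The SAP also gives event counts, by-visit laboratory statistics and listings, none of which uses this denominator. This stands too: only the exposure-adjusted secondary AE tables are in question.

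**Higher doses would look safer.** A reader might infer this because raised-dose time falls mostly late. The tables planned do not bear it out to any great extent. SAP 4.1 gives 80 IU/kg no summary column of its own, SAP 4.14 assumes that a minority (for example, under 20%) are raised, and the illustrative coverage above is 59% against 57%. It reaches 68% against 57% only if every raised subject extends.

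**The protocol's own Extension summary shares the fault.** A reader might infer this as well, but an Extension-only summary separates the two levels of sampling. It is the SAP's joint presentation that removes the split.

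**Conclusion.** The point holds, within limits. Exposure-adjusted rates of laboratory-derived AEs, per subject-year and per injection, are diluted by Extension time in which the readable text schedules little or no testing, and SAP 4.14 drops the separate Extension summary that would have shown it.

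The percentages in the working are falls in scheduled sampling. They carry over to event rates only if detection is proportional to scheduled samples, which is an assumption; persistent abnormalities and clinically indicated tests would make the fall in event rates smaller. They also rest on 100 and 50 subjects with full follow-up, and on the visit narrative matching the unreadable rows of the schedule table. The direction survives full panels at all three redacted visits.

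Percentage-of-subjects tables, by-visit laboratory summaries and the anti-C1-INH antibody primary endpoint are not affected in this way. Any effect on the dose comparison is likely small. This is an inexpensive improvement to the reporting of secondary safety results, and it does not undermine the primary analysis.

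**What to change.** In SAP 4.7.2.1:
- Show the exposure-adjusted rates (per subject-year and per injection) of laboratory-derived AEs in separate columns for Treatment Periods 1 and 2 and for the Extension. Define these as AEs that the investigator recorded from clinically significant laboratory values, following the coding in Protocol 10.3.
- Keep all Extension events, including those from clinically indicated tests and the Week 88 urinalysis. Restricting the rate to Treatment Periods 1 and 2 would discard real long-term events.
- Give the number of scheduled samples per subject-year for each panel in each column.
- Footnote the panels not scheduled in the Extension, so that a low Extension or pooled rate is not read as evidence of safety.

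This restores, for these AEs, a split that the protocol already planned, and it changes no visit, sample or treatment. The cost is SAP wording and extra table columns. The Treatment Period 1 and 2 rates will be higher, and less precise, than the pooled ones.

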3.5 Planned Number of Subjects

The study plans to enroll subjects who complete participation in CSL830_3001. Additional subjects who have not participated in study CSL830_3001 will be enrolled so that the total number of subjects randomized is approximately 110.

Assuming that up to 10% of subjects withdraw before the completion of the study, 100 subjects are planned to complete the study.

Subjects from the United States who have completed Treatment Period 1 and Treatment Period 2 according to the study protocol are eligible to enroll in the Extension Period. Approximately 50 of these subjects are anticipated to enroll in the Extension Period.

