9.2.2 Solicited Local Adverse Events (Injection Site Reactions)

Solicited local AEs are injection site reactions at the CSL830 injection site that are specifically asked for and recorded.

Subjects will record the occurrence of local AEs (injection site reactions) in their eDiary by answering the following question: “Have you experienced any local reactions at the injection site (eg, discomfort, swelling, bruising, or itching)? (yes/no)”. Subjects will be instructed to take notes (outside of the diary) to describe any local AEs they experience and to report that information to their investigator. Each investigator will use the information from the diary and the subject to identify and grade the intensity of each symptom. Each symptom will be entered as an independent AE.

Solicited local AEs are defined and graded as follows:

Table 11: Intensity of Solicited Local Adverse Events

Solicited Local Adverse Event	Intensity Grading		
	Mild (Grade 1)	Moderate (Grade 2)	Severe (Grade 3)
Discomfort at the injection site after the injection procedure (eg, pain, burning)	Present but does not interfere with activity	Repeated use of non-narcotic pain reliever for over 24 hours or interferes with activity	Any use of narcotic pain reliever or prevents daily activity
Swelling at the injection site worse than at the end of the injection procedure	Up to 2.5 cm larger than at the end of the injection procedure and does not interfere with activity	2.6 to 5.0 cm larger than at the end of the injection procedure or interferes with activity	Over 5.0 cm larger than at the end of the injection procedure or prevents daily activity
Bruising at the injection site	Up to 2.5 cm	2.6 to 5.0 cm	Greater than 5.0 cm
Itching at the injection site	Present but does not interfere with activity	Interferes with activity	Prevents daily activity

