CSL830 will be administered as a single SC injection twice weekly at home either independently (i.e., self-administered by the subject) or with assistance (i.e., with the help of a caretaker such as a parent or guardian) during Treatment Period 1 and Treatment Period 2.

During the study, an investigator may increase a subject’s CSL830 dose if that subject is eligible for dose increase. A subject’s eligibility for a dose increase is related to the frequency of his or her HAE attacks. The rules for a dose increase are different during the “fixed dose” Treatment Period 1 and the “dose optimization” Treatment Period 2.

Dose increase rules are presented in [Section 3.2](#).

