3.3 Study Schedule

3.3.1 Planned study duration

The duration of the study for an individual subject who does not participate in the Extension Period is expected to be up to 58 weeks. This estimation is based on:

- A Screening Period lasting up to 4 weeks (≤ 28 days), as needed.
- Two treatment periods totaling 52 weeks (367 days \pm 2 days).
- A Follow-up Period lasting 2 weeks (14 days \pm 3 days).

The overall study duration (i.e., from the first subject's first Screening Visit to the last subject's Follow-up Visit) is planned to be 26 months, but will depend on recruitment.

US-subjects will have the opportunity beyond the Week 53 Visit to enter into an Extension Period of up to 90 weeks. The Extension Period will comprise a treatment period of 88 weeks and a follow-up period of 14 days \pm 3 days (see Country-Specific Protocol Amendment No. 1 (United States), dated 10 July 2015).

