- Summary of AEs that are included in one of the following SMQs that will be used to screen for hypersensitivity (number of subjects with AEs, with SAEs, with events occurring within 24 hours of investigational product administration, with temporally-related AEs, related events, events leading to study discontinuation, with each severity and with each outcome). Potential events of hypersensitivity are identified using the following SMQs:
 - SMQ = ‘Hypersensitivity (SMQ)’ and selected = ‘Broad’.
 - SMQ = ‘Anaphylactic reaction (SMQ)’ and selected = ‘Broad’.
 - SMQ = ‘Anaphylactic/anaphylactoid shock conditions (SMQ)’ and selected = ‘Broad’.

Incidence of subjects with AEs that are included in one of the above defined SMQs that will be used to screen for hypersensitivity by SOC and PT.

Anaphylactic events will be classified as an AE of special interest (AESI)

The number of subjects experiencing non-serious AEs, non-serious unsolicited AEs and non-serious solicited AEs which occur in at least one treatment in at least 1, 2, 3, 4 and 5% of events will also be presented.

A summary table for AEs occurring within 24 hours after administration of rescue medication for the treatment of HAE attacks will be presented by SOC and PT. Rescue medications are defined as Firazyr, Cinryze, Berinert, Kalbitor, Ruconest, Fresh Frozen Plasma, others.

By-subject listings will be produced for all AEs, related AEs, SAEs, AEs Leading to Study Discontinuation, AE PT ‘Embolic and Thrombotic Events’, AE High Level Term ‘Sepsis, Bacteraemia, Viraemia and Fungaemia NEC’ and for AE PT ‘Anaphylactic Reaction’ (SMQ) and ‘Anaphylactic / Anaphylactoid Shock Conditions’ (SMQ).

Solicited AEs

Solicited AEs are investigational product injection site reactions (i.e., local reactions, including pain, swelling, bruising, itching, erythema or other) selected using the MedDRA high level term (HLT) = “injection site reactions” but excluding those reactions which have been determined to be injection site reactions following an injection of a non-investigational product. All solicited AEs will be reviewed for their AE term verbatim. If the AE verbatim term contains the name of a non-investigational product (i.e. Firazyr, Cinryze, Berinert, Kalbitor, Ruconest, Fresh Frozen Plasma, others), the AE will be excluded from the solicited AE tables.

The following summaries of solicited AEs will be produced:

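### The SAP's frequency-threshold tables of non-serious AEs count subjects but select terms by share of events, so terms can land in the wrong tier (minor)

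*SAP*

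**What the plan says.** SAP 4.7.2.1 (Method of analysis for secondary safety endpoints) describes a set of threshold tables. What is displayed is "The number of subjects experiencing non-serious AEs, non-serious unsolicited AEs and non-serious solicited AEs". The condition for a term to be shown follows in the same sentence: "which occur in at least one treatment in at least 1, 2, 3, 4 and 5% of events will also be presented". No part of the SAP or protocol redefines this base or says which events form the denominator for each of the three sets. The table shells are in a separate document (SAP 5.3).

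Elsewhere the SAP works with subjects. The opening of 4.7.2.1 says the AE tables give the number of subjects with an AE, the "percentage of subjects based on the Safety Population, and number of events". The notes in SAP 4.7 count a subject with repeats of one preferred term once for that term. SAP 4.7.2.1 also plans tables with no cut-off, such as "Incidence of subjects with AEs by SOC and PT", with matching tables for solicited and for unsolicited AEs.

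Two features of the trial allow many events per subject. On local reactions, protocol 9.2.2 states: "Each symptom will be entered as an independent AE". On dosing, SAP 3.1.3 states: "CSL830 will be administered as a single SC injection twice weekly at home".

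**The concern.** A frequency-threshold table is read as showing which AEs are common among patients. A cut-off on share of events answers a different question: how large one term is relative to everything else recorded. When events cluster within subjects, the two can differ widely. A term affecting many subjects once each is diluted by other subjects' repeated events, while a term repeated by one subject gains share. The count-once rule in SAP 4.7 prevents this in the subject counts, but the event-based cut-off bypasses it at the selection step.

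At stake is which terms appear at the 1, 2, 3, 4 and 5% tiers, and so how anyone reading only those tables would judge the common non-serious AEs.

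**Working it through.** The plan gives no computed figure for this rule, so there is none to reproduce. The check compares the two shares directly.

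**Inputs from the documents**
- Randomized: "the total number of subjects randomized is approximately 110" (protocol 3.5). Allocation is balanced over two starting doses (SAP 3.6), so about 110 / 2 = 55 per arm.
- Duration: "Two treatment periods totaling 52 weeks" (SAP 3.3.1). At two injections a week, 2 × 52 = 104 per subject and 55 × 104 = 5,720 per arm.

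**Assumptions (the documents give no event rates)**
- 0.02 to 0.50 solicited events per injection.
- 2, 4 or 8 unsolicited events per subject, that is 110, 220 or 440 per arm.
- All events counted are non-serious, and dose increases are ignored.

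**Formulas**
- Total events E = 5,720 × solicited rate + unsolicited events.
- Event share = events of the term / E.
- Subject share = subjects with the term / 55.

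**Results for the all-non-serious set.** Term A occurs once each in 11 of 55 subjects (subject share 20%). Term B is one local symptom in one subject after all 104 injections (subject share 1/55 = 1.8%).

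| Solicited events per injection | Solicited events | E (2 to 8 unsolicited per subject) | Term A, 11/E | Term B, 104/E |
|---|---|---|---|---|
| 0.02 | 114.4 | 224.4 to 554.4 | 4.90% to 1.98% | 46.3% to 18.8% |
| 0.05 | 286 | 396 to 726 | 2.78% to 1.52% | 26.3% to 14.3% |
| 0.10 | 572 | 682 to 1,012 | 1.61% to 1.09% | 15.2% to 10.3% |
| 0.20 | 1,144 | 1,254 to 1,584 | 0.88% to 0.69% | 8.3% to 6.6% |
| 0.50 | 2,860 | 2,970 to 3,300 | 0.37% to 0.33% | 3.5% to 3.2% |

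- Term A misses 5% in every row, and from 0.20 upward it misses every tier.
- Term B reaches 5% whenever E ≤ 104 / 0.05 = 2,080, which is every row but the last. In the last row it still reaches 1, 2 and 3%. Term B is an extreme case. With half as many repeats and E = 286 + 220 = 506, the share is 52/506 = 10.3%.
- At E = 506, a once-per-subject term needs 0.05 × 506 = 25.3, so 26 of 55 subjects (47%), to reach 5%. A subject rule needs 0.05 × 55 = 2.75, so 3 of 55.

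**If each set uses its own events as denominator** (the SAP does not say), local reactions no longer dilute the unsolicited set. Term A is then 11/110 = 10%, 11/220 = 5.0% or 11/440 = 2.5%, so it can reach 5%. The mismatch remains: reaching 5% takes 0.05 × 110 = 5.5, so 6 subjects (11%), up to 0.05 × 440 = 22 subjects (40%).

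**Qualifying in at least one treatment.** Taking the 11 subjects within one arm already favours Term A. Apart from events on 80 IU/kg, the ≥ 40 IU/kg share is a weighted average of the two dose-column shares, so it cannot exceed the larger.

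**Extension Period.** The SAP analyses it jointly. It raises the possible injections to 2 × (52 + 88) = 280 for a subject who completes it, which gives more room for repeats than the 104 used here.

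**The case against.** The strongest reply is that nothing is lost. Subject-incidence tables by SOC and PT are planned without a cut-off for all, solicited and unsolicited AEs, and by-subject listings follow. The threshold tables are an addition that the protocol's safety analysis (11.3.3.2) does not ask for. That stands, and it sets the weight of the point. A reader might infer that common systemic AEs vanish from the safety reporting, or that these are the tables from which common AEs will be reported. The documents support neither.

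Second, the tables show numbers of subjects, so a term driven by one subject would appear with a count of one. That also stands. It limits how far a reader could be misled by an included term, but does nothing for a term left out of a tier.

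Third, a reader might infer that injection-site symptoms dominate the events in this trial. The documents do not say so. Protocol 1.4 reports local reactions in only a small proportion of subjects in an earlier study. The solicited rate is therefore varied above, and Term A misses the 5% tier of the all-non-serious set even at the lowest rate.

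Fourth, the event base may simply be a slip, since the sentence counts subjects and the section's own convention is a subject base. That is quite possible, and the unseen table shells may already be right. It is a reason to correct the phrase: as written, a programmer would use events.

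**Conclusion.** The point holds as a minor inconsistency. The selection rule uses a different unit from the tables it governs and from the SAP's own AE convention. Under the stated assumptions, a term in 20% of an arm, once per subject, is 0.33% to 4.9% of all non-serious events and always misses the 5% tier. One subject reacting at every injection contributes 3.2% to 46%. The size depends on event rates that the documents do not give, on about 55 subjects per arm over 52 weeks, and on whether each set has its own event denominator. The consequence is confined to which tier of the threshold tables a term reaches, if any. Neither the primary endpoints nor the tables without a cut-off are affected.

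**What to change.** In SAP 4.7.2.1, replace *of events* with *of subjects in the Safety Population in that treatment*, and state that this denominator applies to all three sets (all, unsolicited and solicited non-serious AEs). Check the table shells for the same wording.

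The cost is one phrase and one denominator in the program, with no new data. There is a small downside. With about 55 subjects per starting dose, one subject is 1/55 = 1.8%, so the 1% tier filters nothing in the 40 and 60 IU/kg columns. The other tiers also become coarse: 2% and 3% both mean 2 subjects (1.1 and 1.65 rounded up), and 4% and 5% both mean 3 (2.2 and 2.75 rounded up). Under the new rule Term B counts once, at 1.8%, and no longer reaches the 2 to 5% tiers.
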